11.1.4 Unexpected Adverse Event

For this study, an AE is considered unexpected when it varies in nature, intensity or frequency from information provided in the current IB, package insert, or when it is not included in the informed consent document as a potential risk. Unexpected also refers to AEs that are mentioned in the IB as occurring with a class of drugs or are anticipated from the pharmacological properties of the drug, but are not specifically mentioned as occurring with the particular drug under investigation.

11.1.5 Relatedness

AEs will be categorized according to the likelihood that they are related to the study drug(s). Specifically, they will be categorized using the following terms:

Unrelated	The Adverse Event is not related to the drug(s)
Unlikely	The Adverse Event is doubtfully related to the drug(s)
Possible	The Adverse Event may be related to the drug(s)
Probable	The Adverse Event is likely related to the drug(s)
Definite	The Adverse Event is clearly related to the drug(s)

11.2 Adverse Event (AE) Recording

- Adverse events (AEs) will be recorded from the time of consent until 100 days after treatment discontinuation of study drugs, or until a new anti-cancer treatment starts, whichever occurs first.
- AEs will be recorded regardless of whether or not the event(s) are considered related to the study drugs.
- All AEs will be recorded in the subject's medical record and on the appropriate study specific eCRF form within the EDC system.
- All AEs considered related to study drugs will be followed until resolution to \leq Grade 1 or baseline, deemed clinically insignificant, and/or until a new anti-cancer treatment starts, whichever occurs first.

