6.3.2 Nivolumab Dose Delay Criteria

Adverse events (both non-serious and serious) associated with nivolumab exposure may represent an immunologic etiology. These adverse events may occur shortly after the first dose or several months after the last dose of treatment. Nivolumab must be withheld for drug-related toxicities and severe or life-threatening AEs as per Table 3 below. See Section 5.4 for supportive care guidelines, including use of corticosteroids. **NOTE:** In addition to information in the table, permanently discontinue for any severe or Grade 3 drug-related AE that recurs or any life-threatening event. Subjects with intolerable or persistent Grade 2 drug-related AE may have study medication held at physician discretion. Permanently discontinue study drug for persistent Grade 2 adverse reactions for which treatment with study drug has been held, that do not recover to Grade 0-1 within 6 weeks of the last dose unless delay beyond 6 weeks allows for prolonged steroid taper to manage toxicity. In such cases, the Sponsor Investigator must be consulted prior to re-initiating treatment.

Table 3: Nivolumab dose modification guidelines for drug-related adverse events

Toxicity	Hold Treatment For	Timing for Restarting Treatment	Discontinue Subject
Diarrhea/Colitis	Grade 2-3	Toxicity resolves to Grade 0-1	Toxicity does not resolve within 6 weeks of last dose unless delay beyond 6 weeks allows for prolonged steroid taper to manage toxicity. In such cases, the Sponsor Investigator must be consulted prior to re-initiating treatment.
	Grade 4	Permanently discontinue	Permanently discontinue
Pneumonitis	Grade 2	Toxicity resolves to Grade 0-1	Toxicity does not resolve within 6 weeks of last dose unless delay beyond 6 weeks allows for prolonged steroid taper to manage toxicity. In such cases, the Sponsor Investigator must be consulted prior to re-initiating treatment.
	Grade 3-4	Permanently discontinue	Permanently discontinue
Hepatitis	≥ Grade 2 if subject has baseline AST, ALT or total bilirubin that is within normal limits; ≥ Grade 3 if subject has baseline AST, ALT or total bilirubin within the Grade 1 toxicity range	Toxicity resolves to Grade 0-1	Toxicity does not resolve within 6 weeks of last dose unless delay beyond 6 weeks allows for prolonged steroid taper to manage toxicity. In such cases, the Sponsor Investigator must be consulted prior to re-initiating treatment.

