7 STUDY CALENDAR & EVALUATIONS

Study Day [Cycle = 14 days]	Screen	Cycle 1	Cycle 2 +	Safety Follow up ¹⁴	Safety Follow up ¹⁴	Long Term Follow Up ¹⁵
	-28 days	Day 1 (± 3)	Day 1 (± 3)	30 days (±7)	90 days (±7)	Q 3 months (±14 days)
REQUIRED ASSESSMENTS						
Informed Consent/HIPAA auth.	X					
Medical History ¹	X					
Physical Exam	X	X	X	X		
Vital Signs including ECOG PS ²	X	X	X	X		
AE Assessment and Con Meds	X	X	X	X	X	
LABORATORY ASSESSMENTS						
Blood Chemistries ³	X	X ¹³	X	X		
Thyroid Function Testing ⁴	X	X ¹³	X	X		
PT/INR and aPTT	X	X ¹³	X	X		
Platelets, ANC & Hgb	X	X ¹³	X	X		
Urinalysis	-7d ⁵	X ¹³	X			
Pregnancy Test for WOCP ⁶	X	-24h	X ⁶			
DISEASE ASSESSMENT						
CT or MRI chest, abdomen/pelvis ⁷	X		X			X
CT or MRI Brain, if indicated ⁷	[X]					
TREATMENT						
Nivolumab		X	X			
Ramucirumab		X	X			
CORRELATIVE STUDIES						
CT-guided biopsy ⁸	X		X ⁸			
Whole Blood for Somatic Baseline ⁹		X				
Serum for soluble PD-L1 analysis ⁹		X	C5D1			
BANKING SAMPLES						
Whole Blood ¹⁰ - Optional		X				
Serum and Plasma ¹¹ - Optional		X		X		
Unstained Slides ¹² - Optional		X	X ¹²			
FOLLOW UP						
Survival status, additional cancer therapy						X

Footnotes:

1. Medical history to include demographics, prior treatments, radiation and surgical history. Other information obtained during the medical history includes: Smoking history to include: amount, frequency, start and stop dates of cigarette, cigar and pipe usage. A question about how the patient heard about the study. Prior genetic or biomarker testing results will be required if available.
2. Vital signs to include BP, HR, weight, height (screening) only. In addition, ECOG performance status should be obtained.
3. Blood Chemistries to include: sodium, potassium, blood urea nitrogen (BUN), serum creatinine (or GFR; see 3.1.7), calcium, albumin, ALT, AST, bilirubin, alkaline phosphatase (ALK), total protein, glucose.
4. Thyroid studies will be obtained every 3 cycles (about 6 weeks) starting with Cycle 4 (\pm 7 day window). The type of testing performed (TSH, T3 free vs direct, or T4 free vs direct) should be per local standards.
5. Within 1 week of study registration. If urine dipstick or routine analysis is $\geq 2+$, a 24-hour urine collection for protein must demonstrate < 1000 mg of protein in 24 hours to allow participation in this protocol.

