14. Safety Follow Up Visits: 30 days (± 7) post last dose of study treatment. For subjects with unresolved treatment related toxicity, follow as medically appropriate until resolution or stabilization. Day 90 AE and conmed assessment may be done by phone, email or other avenues as appropriate.
15. Long-term follow up: Every 3 months until 2 years from initiation of study therapy. Follow up may be accomplished by phone call, email, local physician's record. Disease assessment will be performed per physician's discretion. Results of all disease assessment should be captured. If the patient progresses, they should be followed for survival and/or initiation of anti-cancer therapy.

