11.3 Serious Adverse Event (SAE) Reporting

11.3.1 Site Requirements for Reporting SAEs to HCRN

- SAEs will be reported from time of signed informed consent until **100** days after discontinuation of study drug(s) or until a new anti-cancer treatment starts, whichever occurs first.
- SAEs will be reported on the SAE Submission Form and entered in the SAE tab in the EDC system **within 1 business day** of discovery of the event.
- SAEs will be reported whether or not they are related to the study drug(s).
- All SAEs will be recorded in the subject's medical record and on the appropriate study specific eCRF form within the EDC system.
- All SAEs regardless of relation to study drug will be followed until resolution to \leq Grade 1 or baseline and/or deemed clinically insignificant and/or until a new anti-cancer treatment starts, whichever occurs first.

Additionally, any serious adverse event, considered by an investigator to be related to either study drug, which is brought to the attention of the investigator at any time outside of the 100-day time period specified above, also must be reported immediately to HCRN.

The site will submit the completed SAE Submission Form to HCRN **within 1 business day** of discovery of the event. The form may be sent electronically to [contact]. The investigator is responsible for informing the IRB and/or the Regulatory Authority of the SAE as per local requirements. The original copy of the SAE Submission Form and the email correspondence must be kept within the study file at the study site.

Once the SAE has resolved, sites must submit a follow up SAE Submission Form within a reasonable timeframe to HCRN electronically to [contact].

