11.3.5 Potential Drug Induced Liver Injury (DILI)

Wherever possible, timely confirmation of initial liver-related laboratory abnormalities should occur prior to the reporting of a potential DILI event. All occurrences of potential DILIs, meeting the defined criteria, must be reported as SAEs.

Potential drug induced liver injury is defined as:

1. An elevated AST or ALT lab value that is greater than $3 \times$ the upper limit of normal, **and**,
2. an elevated total bilirubin lab value that is greater than $2 \times$ the upper limit of normal without initial findings of cholestasis (elevated serum alkaline phosphatase), **and**,
3. No other immediately apparent possible causes of aminotransferase (ALT or AST) elevation and hyperbilirubinemia, including, but not limited to, viral hepatitis, pre-existing chronic or acute liver disease, or the administration of other drug(s) known to be hepatotoxic.

DILIs that occur in any subject from the date of first dose through 100 days following discontinuation of dosing, whether or not related to Eli Lilly and Company's product and/or BMS's product, must be reported **within 1 business day** to HCRN. The site will submit a completed SAE Submission Form to HCRN **within 1 business day** of discovery of the event. The form may be sent electronically to [contact].

HCRN will report the event **within 1 business day** to Eli Lilly and Company (Attn: Global Patient Safety; [contact] or [contact]) and BMS (Attn: Global Pharmacovigilance & Epidemiology; [contact]; [contact]).

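### AE, SAE and liver-injury capture runs to 100 days after treatment, but the last scheduled AE assessment is Day 90 (±7), leaving 3 to 17 days without a scheduled enquiry

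*Combined protocol and SAP*

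**What the plan says.** **Recording and reporting windows.** Section 11.2: "Adverse events (AEs) will be recorded from the time of consent until 100 days after treatment discontinuation of study drugs", closing early if new anti-cancer treatment begins. The scope is wide: "AEs will be recorded regardless of whether or not the event(s) are considered related to the study drugs". Section 11.3.1: "SAEs will be reported from time of signed informed consent until" the same 100-day point, with the same early closure. Section 11.3.5 covers "DILIs that occur in any subject from the date of first dose through 100 days following discontinuation of dosing" and gives no early closure for new treatment.

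**Scheduled enquiry.** In the section 7 calendar the row "AE Assessment and Con Meds" is marked at screening, Cycle 1, Cycle 2 onward, the 30-day safety visit and the 90-day safety contact. Both safety contacts carry a ±7-day window. The row is blank under long-term follow-up. Footnote 14 adds: "Day 90 AE and conmed assessment may be done by phone, email or other avenues as appropriate".

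**Long-term follow-up.** Footnote 15 and the calendar provide for contact every 3 months (±14 days) until 2 years from the start of therapy. The content is survival, further cancer therapy and discretionary disease assessment.

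**Late events and analysis.** Section 6.3.2 says of nivolumab events: "These adverse events may occur shortly after the first dose or several months after the last dose of treatment". Section 12.5 tabulates the proportion of subjects by AE grade, with 95% confidence intervals.

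**The concern.** Three safety sections agree on 100 days, but the calendar that sites work from stops asking earlier. A site can follow the calendar exactly and still hold no solicited AE information for the end of the period that section 11 tells it to cover. What it records for those days depends on whether the subject volunteers an event or the site learns of it some other way, and that may differ between sites.

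Characterising adverse effects is a secondary objective, and one of the two drugs is described as causing events after treatment has ended, so the tail of the window is not a formality. At stake is the completeness of late AE data in a 35-subject safety summary.

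**Working it through.** The plan states no figure for this gap, so there is none to reproduce. The check is day arithmetic, followed by a search for any other provision that covers the same days.

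**Inputs**
- End of window: E = 100 days after discontinuation (sections 11.2, 11.3.1, 11.3.5).
- Last scheduled AE contact: d = 90 ± 7, so Day 83 to Day 97 (section 7).
- Lag between last dose and the date of discontinuation: L. Footnote 14 counts its safety visits from the last dose, while section 11 counts from discontinuation. L = 0 is an assumption.

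**Formula:** uncovered days = L + E − d.

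| Contact on | L = 0 | L = 14 (one cycle, assumed) |
|---|---|---|
| Day 97 | 100 − 97 = 3 | 17 |
| Day 90 | 100 − 90 = 10 | 24 |
| Day 83 | 100 − 83 = 17 | 31 |

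**Does anything else cover these days?**
- *Footnote 14, unresolved toxicity.* It follows treatment-related events already known. It does not look for new ones.
- *Section 11.3.1, late SAEs.* The extra duty covers a related SAE "which is brought to the attention of the investigator at any time outside of the 100-day time period specified above". It is passive, limited to related serious events, and applies outside the 100 days.
- *Long-term follow-up.* There is no AE mark. The documents do not say from which day the 3-month interval runs. Taking 3 months as 91 days, a contact falls on Day 107 to 135 if counted from the Day 30 visit (30 + 91 ± 14), or Day 167 to 195 if counted from the Day 90 contact (90 + 91 ± 14). Either could pick up an event by chance, but neither is asked to.
- *Subjects completing treatment.* Treatment may last 24 months, and long-term follow-up ends 2 years from initiation. For these subjects no contact is scheduled after the Day 90 call.
- *New anti-cancer treatment.* If it starts before the Day 90 contact, the AE and SAE windows are already closed and there is no AE/SAE gap.

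**Is the stopping rule touched?** Section 12.2 counts related grade 5 toxicity in the first 4 cycles, which is 4 × 14 = 56 days without delays. The uncovered days begin more than 83 days after the last dose, so they fall outside it. The response endpoint and its sample size do not use AE data.

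**Check of the remedy (L = 0).** A contact on or after Day 100 leaves 0 uncovered days. Day 100 with the present ±7 window runs from Day 93 to Day 107 and still leaves up to 100 − 93 = 7 days.

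**The case against.** The strongest reply is that a recording window may properly outlast the last solicited contact. Section 11 creates a duty to record and report what is discovered, and SAEs are due within 1 business day of discovery, not at a visit. Deaths come to light through survival follow-up while that runs, and known related toxicities are followed. What remains uncovered is mainly new AEs, non-serious or unrelated ones above all, arising between the last contact and Day 100. This stands, and it limits the point. A reader might infer that events in those days are never ascertained, or that sites cannot meet section 11.2. The documents support only that no AE assessment is scheduled for them.

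A reader might also take the 3 to 17 days as 3% to 17% of post-treatment AEs missed. That needs events spread evenly over 100 days, which nothing in the plan supports. As a share of all recording time the gap is smaller. With an assumed 8 weeks on treatment (56 + 100 = 156 days) it is 3/156 to 17/156, or 2% to 11%. At 24 months (about 730 + 100 = 830 days) it is 0.4% to 2%. These too are shares of days, not of events.

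Nor does section 12.5 define a rate to 100 days that would be biased by a known amount. A missed late event changes a cell of the table only if that subject had no earlier event counted there.

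The section 6.3.2 warning gives limited support, since events several months out may fall beyond Day 100 as well.

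Section 6 asks for AE evaluation at every study visit, and that could be read as reaching long-term follow-up. But the calendar leaves that cell blank, and the contact may be no more than a local physician's record.

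**Conclusion.** The mismatch is real and no other provision closes it. For subjects not yet on new therapy, 3 to 17 days of the 100-day window (10 at the nominal day) have no scheduled AE enquiry. The figure assumes both clocks start at the last dose; a later discontinuation date widens the gap by that lag.

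The consequence is possible, modest under-recording of late AEs in a secondary safety summary. Its size in events cannot be derived from the documents. This is a correction worth making, not a threat to the trial's main conclusion.

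**What to change.** Reconcile the section 7 calendar column and footnote 14 with sections 11.2, 11.3.1 and 11.3.5. One way is to move the existing remote contact to Day 100 or later with a forward-only window (for example Day 100 to Day 107), asking about AEs through Day 100. Keeping a symmetric ±7 window would not close the gap.

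In the same edit:
- State one anchor, the last dose, for both the safety contacts and the 100-day windows.
- Align the concomitant-medication question at that contact with section 5.5.1. That section records such medication to 30 days after the last dose and beyond that only for SAEs, whereas the calendar marks it at Day 90 without that limit.

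The cost is calendar wording and the same single contact about 10 days later, with no added visit. Recall since the Day 30 visit lengthens from 60 days (90 − 30) to 70 (100 − 30) at the nominal days. One limit remains: the calendar marks no blood chemistry after the 30-day visit, so a later remote contact can ask about liver events but will not itself detect the laboratory changes that section 11.3.5 uses to define them.

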11.3 Serious Adverse Event (SAE) Reporting

11.3.1 Site Requirements for Reporting SAEs to HCRN

- SAEs will be reported from time of signed informed consent until **100** days after discontinuation of study drug(s) or until a new anti-cancer treatment starts, whichever occurs first.
- SAEs will be reported on the SAE Submission Form and entered in the SAE tab in the EDC system **within 1 business day** of discovery of the event.
- SAEs will be reported whether or not they are related to the study drug(s).
- All SAEs will be recorded in the subject's medical record and on the appropriate study specific eCRF form within the EDC system.
- All SAEs regardless of relation to study drug will be followed until resolution to \leq Grade 1 or baseline and/or deemed clinically insignificant and/or until a new anti-cancer treatment starts, whichever occurs first.

Additionally, any serious adverse event, considered by an investigator to be related to either study drug, which is brought to the attention of the investigator at any time outside of the 100-day time period specified above, also must be reported immediately to HCRN.

The site will submit the completed SAE Submission Form to HCRN **within 1 business day** of discovery of the event. The form may be sent electronically to [contact]. The investigator is responsible for informing the IRB and/or the Regulatory Authority of the SAE as per local requirements. The original copy of the SAE Submission Form and the email correspondence must be kept within the study file at the study site.

Once the SAE has resolved, sites must submit a follow up SAE Submission Form within a reasonable timeframe to HCRN electronically to [contact].

11.3.2 HCRN Requirements for Reporting SAEs to Eli Lilly

HCRN will submit all at least possibly related SAEs (including DILI, overdose, pregnancy, etc.) received from sites to Eli Lilly **within 7 business day** of receipt of the SAE Reporting Form and to regulatory authorities (FDA) per federal guidelines.

HCRN will fax or email a SAE Submission Form for all SAE reports and any other relevant safety information to Eli Lilly and Company (Attn: Global Patient Safety; [contact] or [contact])

HCRN will provide follow-up information to Eli Lilly and Company Global Patient Safety as reasonably requested.

11.3.3 HCRN Requirements for Reporting SAEs to BMS

HCRN will submit all SAEs (including DILI, overdose, pregnancy, etc.) received from sites to BMS **within 1 business day** of receipt of the SAE Reporting Form and to regulatory authorities (FDA) per federal guidelines.

HCRN will fax or email a SAE Submission Form for all SAE reports and any other relevant safety information to BMS (Attn: Global Pharmacovigilance & Epidemiology; email: [contact]; [contact]).

HCRN will provide follow-up information to BMS Global Pharmacovigilance & Epidemiology as reasonably requested.

11.3.4 Reporting of Pregnancy

It is the responsibility of site investigators or their designees to report any pregnancy in a subject (spontaneously reported to them), including the pregnancy of a male subject's female partner that occurs during the trial or within 5 months) following the last dose of study drugs for females, and 7 months following the last dose of study drugs for males.. All subjects and female partners of male subjects who become pregnant must be followed to the completion/termination of the pregnancy. Pregnancy outcomes of spontaneous abortion, missed abortion, benign hydatidiform mole, blighted ovum, fetal death, intrauterine death, miscarriage and stillbirth must be reported as serious events (Important Medical Events). If the pregnancy continues to term, the outcome (health of infant) must also be reported.

Such events must be reported **within 1 business day** to HCRN. HCRN will report the event **within 1 business day** to Eli Lilly and Company (Attn: Global Patient Safety; [contact] or [contact]) and BMS (Attn: Global Pharmacovigilance & Epidemiology; [contact]; [contact]).

11.3.5 Potential Drug Induced Liver Injury (DILI)

Wherever possible, timely confirmation of initial liver-related laboratory abnormalities should occur prior to the reporting of a potential DILI event. All occurrences of potential DILIs, meeting the defined criteria, must be reported as SAEs.

Potential drug induced liver injury is defined as:

1. An elevated AST or ALT lab value that is greater than $3 \times$ the upper limit of normal, **and**,
2. an elevated total bilirubin lab value that is greater than $2 \times$ the upper limit of normal without initial findings of cholestasis (elevated serum alkaline phosphatase), **and**,
3. No other immediately apparent possible causes of aminotransferase (ALT or AST) elevation and hyperbilirubinemia, including, but not limited to, viral hepatitis, pre-existing chronic or acute liver disease, or the administration of other drug(s) known to be hepatotoxic.

DILIs that occur in any subject from the date of first dose through 100 days following discontinuation of dosing, whether or not related to Eli Lilly and Company's product and/or BMS's product, must be reported **within 1 business day** to HCRN. The site will submit a completed SAE Submission Form to HCRN **within 1 business day** of discovery of the event. The form may be sent electronically to [contact].

HCRN will report the event **within 1 business day** to Eli Lilly and Company (Attn: Global Patient Safety; [contact] or [contact]) and BMS (Attn: Global Pharmacovigilance & Epidemiology; [contact]; [contact]).

